4. RESEARCH DESIGN AND METHODS

4.1 Design

We will conduct a single-center randomized, controlled, double-blinded trial to determine the effect of amantadine administration in patients resuscitated from cardiac arrest who remain comatose at hospital day 3. The primary outcome will be the rate of awakening (defined as following commands) during hospitalization.

4.2 Recruitment and Informed Consent:

The Post-Cardiac Arrest Service treats over 90% of patients successfully resuscitated from cardiac arrest at UPMC Presbyterian Hospital, ensuring that the PI will care for all potential candidates as part of his clinical duties. Potential subjects who remain comatose for 48 hours will be unable to provide informed consent. Therefore, the investigators will approach family or legally authorized representatives to provide consent as a proxy for the subject. The investigators will already have a relationship with these proxies, and we have previously recruited 50% of potentially eligible subjects into studies in this setting. [30, 31]

4.3 Inclusion and Exclusion Criteria are listed in **Table 2**.

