4.12 Justification for Outcome Measures

We have chosen the rate of awakening as the primary outcome in this study. This short-term outcome is appropriate to determine if a potential for benefit exists. [35] Awakening is a prerequisite for a good neurologic outcome. [17] Persistent coma is the most common reason for withdrawal of care (56%) while multiple organ failure is the etiology of death in a minority (17%) of patients. [2]. Prior literature is hindered by withdrawal of support in patients who remain comatose. Achievement of awakening will likely increase the family's interest in continuing supportive care for this population. Consequently it is **critical** to evaluate rate of awakening and time to awakening in both an intervention and placebo group as delaying time to withdrawal may independently increase the rate of awakening.

Awakening is an appropriate short-term outcome as subjects who awaken survive and comprise all good outcomes by definition of CPC or mRS. Most tend to improve in functional status over the year after hospitalization. [19] Two-thirds of patients who awaken but do not survive to discharge die from multiple organ failure. This investigation proposes an early neurologic intervention that is unlikely to improve other organ failure. Thus, we have chosen a short-term neurologic outcome to maximize detection of a neurologic benefit to this intervention. If the rate of awakening is higher in the treatment arm, the face value of awakening would probably prompt clinicians to adopt the treatment. Furthermore, a larger trial powered to evaluate a treatment effect on long-term functional outcomes might be justified.

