4.13 Daily Examinations

A study physician will complete a neurologic examination upon hospital arrival and again once the subject has rewarmed to a core temperature of $>36^{\circ}\text{C}$. [Table 4] The initial examination is used to determine the category of initial illness severity. [2] Daily examinations will not be performed until sedative medications have been discontinued for at least 40 minutes. [36] Our facility uses propofol for the majority of patients. In subjects receiving continuous infusion of midazolam, the midazolam will be discontinued for 60 minutes before examination. In the rare instance of neuromuscular blockade use, examinations will not be completed until the train of four monitor reads 4/4. Following rewarming, this examination will be completed daily. Prior literature has demonstrated that individual findings are less predictive for outcome in the modern era, thus, no one finding will result in cessation of support. [7, 37, 38]

[figure not shown]

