Kaplan-Meier curves will be generated for time-to-awakening for each treatment group and a log-rank statistic will be used to compare the cumulative probability of awakening across treatment groups. Those participants who are not awake by treatment day 7 will be considered censored observations. A Cox proportional hazards regression model will be used to compare time-to-awakening by treatment group controlling for baseline characteristics that are not balanced through random assignment and stratification variables. The assumptions of the Cox proportional hazards model will be evaluated (proportionality of the hazards model) and if violated, a split analysis will be conducted.

Aim 1, Hypothesis 2: A larger proportion of subjects will awaken during the first 7 days of treatment after administration of amantadine when compared to placebo.

A chi-square test will be used to compare the proportion of participants that are awake at day 7 between the two treatment groups. Logistic regression model will be used to compare the proportions by treatment group controlling for baseline characteristics that are not balanced through random assignment and stratification variables.

Aim 2: Determine if the number of serious adverse events differ between subjects randomized to amantadine and subjects randomized to placebo.

It is anticipated that given the severe critical state of those enrolled in the study, each study participant will have multiple serious adverse events. A t-test (or Wilcoxon test) will be used to compare the means number of serious adverse events that occurred during the 7 days after treatment initiation. A regression model will be used to compare the means after controlling for baseline characteristics that are not balanced through random assignment and stratification variables. The type of regression model will depend in the distribution of the number of serious adverse events and could be a linear regression model, negative binomial model, or Poisson model.

4.15.c Sample Size

The sample size calculations are based on the analysis approach for the primary hypothesis (Aim 1, Hypothesis 1) with a type I error rate of 0.05, a two-sided alternative hypothesis, and 80% power. Based on these assumptions, a sample of 120 (60 per treatment group) will be sufficient to detect a difference of awakening of 30% in the control group and 50% in the active treatment group.

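### Hypothesis 2 concerns awakening at any time in the first 7 days, but its chi-square and logistic analyses are worded as status on day 7, and early discharge has no scoring rule

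*Combined protocol and SAP*

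**What the plan says.** Section 4.15.b gives the hypothesis and its test in adjacent paragraphs. The hypothesis reads: "A larger proportion of subjects will awaken during the first 7 days of treatment after administration of amantadine when compared to placebo". The test reads: "A chi-square test will be used to compare the proportion of participants that are awake at day 7 between the two treatment groups". The logistic model that follows compares the same proportions with adjustment.

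Other places bear on which quantity is meant:

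- Section 4.1 uses a third window: "The primary outcome will be the rate of awakening (defined as following commands) during hospitalization".
- For Hypothesis 1, section 4.15.b compares the cumulative probability of awakening, with this rule for patients without the event: "Those participants who are not awake by treatment day 7 will be considered censored observations".
- Section 4.12 says both "Awakening is an appropriate short-term outcome as subjects who awaken survive and comprise all good outcomes by definition of CPC or mRS" and, later, "Two-thirds of patients who awaken but do not survive to discharge die from multiple organ failure".
- Section 4.13 says of the neurologic examination: "Following rewarming, this examination will be completed daily".
- Section 4.15.c ties the sample size to Hypothesis 1, which it calls primary, "with a type I error rate of 0.05, a two-sided alternative hypothesis, and 80% power". It uses 60 patients per arm and awakening of 30% versus 50%.

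No section says how a patient who awoke and then died, relapsed or went home before day 7 enters the chi-square test, or whether such a patient stays in the denominator.

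**The concern.** Ever having awakened by day 7 and being awake on day 7 are different variables. They agree only if everyone who awakens is still awake and observed on day 7. An analyst who codes the test as written would not estimate the quantity in the hypothesis, and the two Aim 1 analyses could disagree through scoring alone.

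The choice also matters for the rationale in section 4.12. That section picks a short-term neurologic outcome because the drug is not expected to change failure of other organs, and it attributes most deaths after awakening to such failure. Counting those patients as not awake brings the non-neurologic deaths back into the endpoint. Finally, if the definition is left open until the data are seen, the choice between two codings becomes post hoc.

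**Working it through.** **1. The wordings side by side**

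| Place | Event | Window |
|---|---|---|
| 4.1, primary outcome | following commands | hospital stay |
| 4.15.b, Hypothesis 1 | first awakening | to treatment day 7 |
| 4.15.b, Hypothesis 2 as stated | awakening at any time | first 7 days |
| 4.15.b, Hypothesis 2 as tested | being awake | day 7 only |

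Take a patient who follows commands on day 3 and dies on day 6. This is an event in the log-rank test. Under the literal wording of the chi-square test it is a non-event.

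**2. The plan's own figure**

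Inputs from 4.15.c: p1 = 0.30, p2 = 0.50, n = 60 per arm, two-sided 0.05. Chi-square power by the normal approximation, with p̄ the mean of p1 and p2:

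power = Φ{ [ (p2 − p1)√n − 1.96·√(2p̄(1 − p̄)) ] / √(p1(1 − p1) + p2(1 − p2)) }

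= Φ{ [0.20 × 7.746 − 1.96 × 0.693] / 0.678 } = Φ(0.28) = 61%.

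The stated 80% is not reproduced. By this formula 80% needs 186 patients in total. The log-rank version (hazard ratio ln 0.5 / ln 0.7 = 1.94; 72 events; 72/0.40 = 180 patients) gives 63% power at 120. That shortfall is a separate matter. Here 61% serves only as the baseline.

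**3. Illustration: equal loss**

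Assume a share L of awakeners is no longer awake on day 7 and is counted as not awake, with the same L in both arms. The documents give no value for L. At 60 per arm the planning rates imply 18 control and 30 amantadine awakeners.

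| L (assumed) | Control | Amantadine | Difference | Patients reclassified (control / amantadine) | Power |
|---|---|---|---|---|---|
| 0 | 30% | 50% | 20 points | 0 / 0 | 61% |
| 5% | 28.5% | 47.5% | 19 points | 0.9 / 1.5 | 57% |
| 10% | 27% | 45% | 18 points | 1.8 / 3.0 | 54% |
| 15% | 25.5% | 42.5% | 17 points | 2.7 / 4.5 | 50% |

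**4. Illustration: unequal loss**

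- Loss of 10% in control and 20% in amantadine: 27% versus 40%, 13 points, power 32%.
- Loss of 20% in control and 10% in amantadine: 24% versus 45%, 21 points, power 68%.
- If 40% awaken in both arms (no effect), losses of 10% and 20% give 36% versus 32%, a difference of 4 points from scoring alone.

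**5. Illustration: discharge**

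Suppose 10% of awakeners in each arm leave before day 7. Three codings are open:

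- Carried forward as awake: 30% versus 50%, 20 points.
- Counted as not awake: 27% versus 45%, 18 points.
- Dropped as missing: 0.27/0.97 = 27.8% versus 0.45/0.95 = 47.4%, 19.5 points.

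**The case against.** The strongest reply is that the day-7 wording is shorthand. The sentence sits directly under a cumulative hypothesis, and Hypothesis 1 uses similar short wording for patients who have not had the event. On that reading the test already counts everyone who awakened by day 7. This is plausible and cannot be ruled out from the text. It does not remove the need for a correction, because the sentence as written specifies a different variable.

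A reader might go further and infer that the plan scores everyone who awoke and then died, relapsed or left as a failure. The documents do not support that. For death and relapse it follows only from the literal wording. For discharge there is no rule at all.

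The support in section 4.12 is also limited. It shows that some patients awaken and later die in hospital, but not how many or whether any do so by treatment day 7. Another sentence in that section says that those who awaken survive. The two sentences conflict, so neither settles the frequency.

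It is also fair to say that Hypothesis 1, not Hypothesis 2, is named primary and drives the sample size. That limits the impact. It does not remove it, because the primary outcome in section 4.1 is a rate of awakening, which is closer to Hypothesis 2.

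**Conclusion.** The mismatch stands: a cumulative hypothesis is paired with a test worded as status on one day, and early discharge has no scoring rule. How much this would change the result cannot be computed from the documents.

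Under assumed equal losses of 5% to 15% of awakeners, the 20-point difference shrinks to 19 to 17 points, and power falls by about 4 to 11 percentage points from 61%. Two inferences should be resisted. One is that the wording necessarily dilutes the effect: that holds for equal loss, but unequal loss can widen or narrow the contrast. The other is that this issue explains power of 50% to 57% against a planned 80%: most of that gap is already there at 61%, before any loss. The point is worth correcting before unblinding. It does not undermine the time-to-awakening analysis.

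**What to change.** In section 4.15.b, define the binary endpoint as following commands (motor score 4 in Table 4) on at least one daily examination through treatment day 7, among all randomized participants. Then:

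- Count anyone who awoke as a success whatever happens later, and anyone who died or left without awakening as not awakened.
- Use this same event in the chi-square, logistic, Kaplan-Meier, log-rank and Cox analyses.
- Fix one clock start for all of them. Section 4.4 separates assignment from first dose, while 4.15.b counts treatment days, so also say how a randomized patient who is never dosed is handled.
- Reconcile the 7-day window with the hospital-stay window in section 4.1.
- Report day-7 status (awake, comatose, dead, discharged) descriptively.

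The cost is a short definition in 4.15.b and an aligned sentence in 4.1. The daily examinations after rewarming already supply the in-hospital data. The change should be dated before unblinding.

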4.6 Allocation Concealment

Amantadine and placebo will appear identical. Drugs will be only have numerical identifiers when handled by the treating nurse and team. Unblinding can be provided to the treating team by the IDS only after consultation with the principle investigator or in predefined emergency situations. These

situations include severe allergic reactions not attributable to any other drug or unexplained tachydysrhythmia requiring cardioversion.

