4.11 EEG Protocol

We obtain a 22-channel digital EEG with simultaneous video recording on all patients resuscitated from cardiac arrest in our facility. This permits correlation of motor activity with electrographic findings and allows for accurate diagnosis of malignant EEG patterns. Contemporaneous interpretation is provided by the Department of Neurology. Subjects will be classified as demonstrating a malignant pattern or not using standard definitions. **[Table 3]** Locally, the PCAC II illness severity phenotype with malignant EEG patterns has a markedly reduced survival when compared to PCAC II illness severity without malignant EEG patterns.

Thus, subjects will be stratified on PCAC and (in the PCAC II illness severity subjects) presence of malignant EEG pattern prior to randomization. If malignant patterns do develop, we will provide therapy to suppress the EEG and any clinical evidence of seizures. **[Figure 3]** This ensures a standard approach to all subjects in the study. Importantly, subjects with malignant EEG patterns that persist beyond 48 hours are excluded from the study and will not be enrolled.

Figure 3. Standardized antiepileptic treatment algorithm for malignant EEG patterns. (Malignant= GPED's, MSE, NCSE)

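### Aim 2 compares only the pooled count of serious adverse events, which has almost no power for a harm confined to one event type; add a prespecified by-arm table of the events the protocol already names

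*Combined protocol and SAP*

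**What the plan says.** Section 4.15.b states Aim 2 as follows: "Determine if the number of serious adverse events differ between subjects randomized to amantadine and subjects randomized to placebo". It anticipates that "each study participant will have multiple serious adverse events". The planned comparison is then: "A t-test (or Wilcoxon test) will be used to compare the means number of serious adverse events". The window is 7 days from the start of treatment. An adjusted model of the same count follows, which "could be a linear regression model, negative binomial model, or Poisson model". Section 4.15.c gives 60 patients per arm and sizes the trial for Aim 1 only. No background rate, detectable difference or power is stated for Aim 2.

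Elsewhere the protocol names particular events. Section 4.6 allows emergency unblinding in situations that include severe allergic reaction and "unexplained tachydysrhythmia requiring cardioversion". Section 4.11 says: "If malignant patterns do develop, we will provide therapy to suppress the EEG and any clinical evidence of seizures". Table 3 defines the EEG patterns, and the Figure 3 caption lists which of them count as malignant. Malignant EEG is also an exclusion criterion (Table 2) and a stratification factor (4.4, 4.15.a). The supplied text plans no comparison by arm of any of these events after randomization.

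**The concern.** When every patient is expected to have several serious adverse events from the underlying illness, the patient-to-patient spread in the total is large. A drug effect that adds at most one event in a minority of patients shifts the mean by a small fraction of that spread. Moving from t-test to Wilcoxon, or to a Poisson or negative binomial model, does not help much, because all of them analyse the same pooled total.

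At stake is how a null Aim 2 result is read. The trial could contain a clear excess of one important event while the planned test shows nothing, and the analysis section provides no table in which the excess would appear. Choosing event types after unblinding would then be open to the charge of selection.

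**Working it through.** **Inputs from the documents.** 60 per arm, equal allocation (4.15.a, 4.15.c). Two-sided 0.05 is stated for Aim 1 and borrowed here. The outcome is the total count per patient over 7 days (4.15.b).

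**The plan's own figure.** There is none for Aim 2. The 120 in 4.15.c belongs to Aim 1. The usual two-proportion formula for 30% against 50% gives 93 per arm, not 60, but that is a separate matter. Here 60 per arm is taken as given.

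**Assumptions (not in the documents).** Background mean m = 2 to 5 events per patient. Variance m + k·m², with k = 0 (Poisson) to 0.5 (overdispersed). The harm is one event type occurring at most once per patient, in 5% on placebo and 20% on amantadine, so it adds δ = 0.20 − 0.05 = 0.15 events per patient to the mean.

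**Power of the pooled count.** Power ≈ Φ(δ/SE − 1.96) + Φ(−δ/SE − 1.96), with SE = SD·√(2/60).

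| m, k | SD | SE | δ/SE | Power |
|---|---|---|---|---|
| 2, 0 | √2 = 1.41 | 0.258 | 0.58 | 0.089 |
| 3, 0.25 | √5.25 = 2.29 | 0.418 | 0.36 | 0.065 |
| 5, 0.5 | √17.5 = 4.18 | 0.764 | 0.20 | 0.054 |

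Simulated t-tests over the same range agree: 5% to 9%. At m = 3, k = 0.25, simulated power is 6.4% for the t-test and 6.5% for the Wilcoxon test.

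**Power of a direct comparison, 5% against 20%.** The pooled proportion is 0.125.
- SE under no difference: √(2·0.125·0.875/60) = 0.0604.
- SE under the alternative: √((0.05·0.95 + 0.20·0.80)/60) = 0.0588.
- Power ≈ Φ((0.15 − 1.96·0.0604)/0.0588) = Φ(0.54) ≈ 0.70.

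Exact enumeration of the two binomials gives 73% for chi-square and 63% for Fisher.

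**Other assumed harms, 60 per arm.**

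| Event rate | Pooled t-test (simulated) | Direct, chi-square | Direct, Fisher |
|---|---|---|---|
| 5% vs 15% | 5-7% | 46% | 33% |
| 5% vs 20% | 5-9% | 73% | 63% |
| 5% vs 25% | 6-12% | 90% | 85% |

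**What the pooled count can detect.** With 80% power, the smallest detectable difference is (1.960 + 0.842)·√(2/60) = 0.51 SD. That is 0.51·1.41 ≈ 0.7 to 0.51·4.18 ≈ 2.1 extra events per patient. To detect δ = 0.15 it would need n = 2·(1.960 + 0.842)²·SD²/0.15² per arm, about 1,400 to 12,200. The direct comparison needs about 76 per arm.

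**The case against.** **The count test answers the aim as written.** Aim 2 asks about the number of events. A randomised comparison of counts, followed by an adjusted model, addresses that, and it could find a broad increase of about half a standard deviation. A reader might infer that the safety aim cannot be answered at all; the text does not support that. The gap is limited to specific harms.

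**Malignant EEG does not bias Aim 1.** Because a new malignant pattern brings suppressive therapy, a reader might infer that an imbalance would distort the awakening result. If the drug caused the pattern and its treatment delayed command-following, that is part of the drug's total effect, and the intention-to-treat comparison captures it. The EEG data could explain an awakening result but would correct no error in it.

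**The EEG data may be uneven.** Sections 4.11 and 4.14 describe EEG in all patients and continuous monitoring for prognostication. Neither says that monitoring runs through all 7 treatment days, and 4.11 does not say outright that its treatment sentence refers to the period after randomization. If monitoring ends when a patient awakens, detection depends on the primary outcome. This stands, and it shapes the fix.

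**The size rests on assumed rates.** Testing three events with a Bonferroni correction lowers direct power for 5% against 20% to 56% (chi-square) or 47% (Fisher). For a rare event, assumed 1% against 5%, unadjusted Fisher power is about 5%, no better than the pooled test. If each affected patient had three events instead of one, pooled power would rise to about 17-30% (Poisson background). These points stand and argue for estimation in place of further tests.

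**Other sections.** Section 3 is cited but is not in the supplied text, so a listing by event type there cannot be excluded. Section 4.6 gives unblinding situations, not safety endpoints, and nothing supplied calls malignant EEG a drug harm. Nor does the text say how a null result would be worded.

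**Conclusion.** The point holds as a limited gap in the safety analysis. In the supplied text, Aim 2 compares only a pooled count, in patients expected to have several events each. For a harm confined to one event type, power stays close to the 5% false-positive rate: about 5-9% for an assumed 5% against 20%, where a direct comparison would have 63-73%. The low pooled power does not depend on one chosen rate; it follows from the plan's own expectation of multiple events per patient, provided the harm adds at most about one event in a minority. The advantage of a direct comparison does depend on the rate, and it disappears for rare events.

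**What to change.** Keep the count analysis unchanged. Add to 4.15.b, before unblinding:

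1. A by-arm table for the same 7 days, giving the number and proportion of patients with at least one of each event: new or recurrent malignant EEG pattern after randomization (Table 3 definitions, with the malignant set in the Figure 3 caption), "unexplained tachydysrhythmia requiring cardioversion", and severe allergic reaction.
2. Risk differences with 95% confidence intervals, described as estimation and not as hypothesis tests. For 5% against 20% at 60 per arm, the approximate interval is 15 ± 1.96·5.88 = 15 ± 11.5 percentage points.
3. Hours of EEG monitoring by arm beside the malignant EEG row, because detection may depend on how long a patient stays comatose and monitored.
4. A sentence stating that a null result on the count does not exclude a specific harm.

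Malignant EEG may also be shown beside the awakening result, labelled as explanatory only.

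The cost is one prespecified table and a record of EEG monitoring time, if that is not already kept. Sample size, treatment and patient care do not change. The downsides are a few imprecise estimates for rare events and an EEG comparison that unequal monitoring could affect.

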4.15 Statistical Analysis

4.15.a Random Assignment

Those eligible for the study will be randomly assigned with equal probability to the experimental condition (amantadine) or the control condition (placebo). Random assignment will be stratified by cardiac arrest category (PCAC) and presence of malignant EEG patterns (only in those with PCAC II), resulting in four strata: PCAC IV, PCAC III, PCAC II with malignant EEG patterns, and PCAC II without malignant EEG patterns. Survival markedly differs between these strata. [Section 3.C.1.b]

To maximize the probability of a balanced design, assignments will occur in block of two and four within each stratum. To ensure that the research team will be masked to the next treatment assignment, the size of the block will be randomly generated.

Random assignment will occur through the University of Pittsburgh Investigational Drug Service (IDS). Study staff will contact the IDS pharmacist, provide the necessary information (e.g., stratum) and the random assignment will be delivered. Given the volume of clinical studies at the University of Pittsburgh, IDS pharmacy medications and randomization are available 24/7.

4.15.b Data Analysis

The data analysis will begin by describing the baseline characteristics of the population. Summary statistics, such as means, standard deviations and frequencies will be generated. Graphical techniques, such as scatter plots and box plots will be used to evaluate the distribution of the baseline characteristics.

The balance of the baseline characteristics across treatment group will be compared. For discrete characteristics a chi-square tests or Fisher's exact test will be used to compare the proportions across treatment group. For continuous measures, either t-tests or Wilcoxon tests will be used to compare the characteristics across treatment group.

Aim 1, Hypothesis 1: Administration of amantadine after cardiac arrest will decrease time to awakening when compared to placebo during the 7 days of treatment.

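### The stated 80% power is wrong: 60 patients per group give only about 60–63% power for 30% versus 50% awakening at two-sided 0.05

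*Combined protocol and SAP*

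**What the plan says.** Section 4.15.c ties the sample size to Aim 1, Hypothesis 1, that amantadine shortens time to awakening over the 7 treatment days. It sets the error rates as "with a type I error rate of 0.05, a two-sided alternative hypothesis, and 80% power". It then states that "a sample of 120 (60 per treatment group) will be sufficient to detect a difference of awakening of 30% in the control group", with the rate on amantadine put at 50%.

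Section 4.15.b supplies the rest of the design:
- Hypothesis 1 is tested with a log-rank statistic, and patients not awake by treatment day 7 are censored.
- Hypothesis 2, the proportion awake at day 7, is tested with a chi-square test.

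Section 4.15.a gives equal allocation. Section 4.15.c states no hazard ratio, expected number of awakenings, dropout allowance, formula or software.

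**The concern.** A 20-point difference around 40% is a familiar planning case, and 60 per group looks too few for 80% power at two-sided 0.05. All the inputs are stated, so the claim can be checked directly.

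This sentence is the only quantitative justification for the trial size in the text supplied. Section 4.12 presents the study as a test of whether a potential for benefit exists, with a larger trial possibly to follow. If power is overstated, a null result would be read as evidence against a 20-point benefit that the trial could not reliably detect, and that line of work might end for the wrong reason.

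**Working it through.** **Inputs** (sections 4.15.a to 4.15.c): 60 per group, equal allocation, 30% versus 50% awake, two-sided alpha 0.05 (z = 1.960), target power 80% (z = 0.842), censoring at day 7. The sum of the two z values, squared, is 7.849.

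**1. The plan's figure by the log-rank test, assuming proportional hazards**
- Hazard ratio = ln(1 − 0.50) / ln(1 − 0.30) = ln 0.5 / ln 0.7 = 1.943, so its logarithm is 0.664.
- Expected awakenings = 60 × 0.30 + 60 × 0.50 = 18 + 30 = 48.
- Schoenfeld, events needed = 4 × 7.849 / 0.664² = 71.1, so 72.
- Freedman, events needed = 7.849 × [(1.943 + 1) / (1.943 − 1)]² = 76.4, so 77.
- Schoenfeld power at 48 events = Φ(√48 / 2 × 0.664 − 1.960) = Φ(0.342) = 63.4%.
- Freedman power at 48 events = Φ(√48 × 0.943 / 2.943 − 1.960) = Φ(0.261) = 60.3%.
- Patients needed, at 40% awakening overall: 72 / 0.40 = 180, or 77 / 0.40 = 192.5, which is 194 in equal groups.

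A simulation of the log-rank test (20,000 trials, exponential times, censoring at day 7) gave 62.4% power at 60 per group and 79.4% at 90 per group.

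**2. The plan's figure by two proportions (the Hypothesis 2 test)**
- The mean proportion is 0.40, so √(2 × 0.40 × 0.60) = 0.693 and √(0.30 × 0.70 + 0.50 × 0.50) = 0.678.
- n per group = (1.960 × 0.693 + 0.842 × 0.678)² / 0.20² = 93.0, or 186 in total. With continuity correction it is 103 per group.
- Power at 60 per group = Φ[(0.20 × √60 − 1.960 × 0.693) / 0.678] = Φ(0.282) = 61.1%.
- Variants: unpooled variance 62.7%, arcsine 61.6%, exact binomial calculation for the chi-square test 61.8%, Fisher's exact or continuity-corrected test 54.2%.

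**3. Could another reading give 80%?**

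| Reading | Power with 60 per group |
|---|---|
| As written, log-rank | 60–63% |
| As written, chi-square without correction | 61–63% |
| One-sided 0.05, either test | 72–74% |
| 30% and 50% taken as proportions *not* awake (hazard ratio 1.74, 72 events), log-rank | 63–65% |

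Any dropout would lower these figures. None is stated, so none was applied.

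**4. What 60 per group does detect**

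With 30% awake on placebo, 80% power is reached at 54.3% awake on amantadine by Schoenfeld and 55.0% by chi-square. The range across formulas, including Freedman, is about 54–56%. At exactly 30% versus 55%:
- Chi-square needs 60.2 per group.
- Log-rank: the hazard ratio is ln 0.45 / ln 0.70 = 2.24, with 60 × 0.85 = 51 events. Power is 82% (Schoenfeld) or 78% (Freedman).

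**The case against.** The strongest objection is that day-7 rates alone do not fix log-rank power. The hazard ratio of 1.94 follows only under proportional hazards, which section 4.15.c does not state, and section 4.15.b allows for the assumption to fail. Hypothesis 1 also predicts faster awakening, and an earlier pattern on amantadine would help the test. Simulations with daily assessment and final rates of 30% and 50% (3,000 trials each) gave:
- 64% under proportional hazards;
- 75% with amantadine awakenings concentrated early and placebo awakenings spread evenly;
- 85% with amantadine awakenings early and placebo awakenings late.

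So 80% is attainable in principle, and the proportional-hazards assumption has to be declared. But it took strongly opposed timing in the two groups to get there, and the plan assumes nothing of the kind. The chi-square result of 61% does not depend on timing at all.

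Covariate adjustment, which section 4.15.b plans, might also add power. The plan gives no figure for it and does not base the calculation on it.

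The origin of 120 cannot be established. Sixty per group matches 30% versus 55%. Taking 50/30 = 1.67 as the hazard ratio and counting all 120 patients as events also gives 79.9%, although that contradicts censoring at day 7. Both explanations are conjecture, and the conclusion needs neither.

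**Conclusion.** The concern holds. On the plan's own inputs, 120 patients give about 60–63% power by the log-rank or the uncorrected chi-square test, which is 17 to 20 points below the stated 80%. The chance of missing a true 30% versus 50% difference is about 37–40%, nearly twice the planned 20%. Reaching 80% would take about 180–194 patients, at least half as many again.

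The log-rank figures rest on proportional hazards and no dropout. The chi-square figure needs only the two rates and no dropout. Because the two tests agree closely, it makes no difference here whether the primary outcome is read as the rate of awakening (section 4.1) or the time to it (section 4.15.c). The choice of formula moves the answer by about three points and cannot explain the gap.

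**What to change.** Keep 120 patients and replace the sentence in section 4.15.c. Suggested content:

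> With 60 patients per group and 48 expected awakenings by day 7, a two-sided log-rank test at 0.05 has about 63% power (Schoenfeld formula, proportional hazards, no dropout) to detect 30% versus 50% awakening. Power of 80% is reached at about 54% awakening on amantadine.

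If the two-proportion formula is preferred, the figures are 61% and 55%. Either way, name the formula and give the expected number of awakenings. The 54% or 55% should be labelled a detectable difference, because nothing in the documents supports it as the expected effect. If the original calculation assumed a timing pattern or a gain from covariate adjustment, state that assumption and its size.

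Add that a null result will be interpreted through the confidence interval for the treatment effect, not through the planned power.

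The cost is one or two sentences and a less favourable figure. No extra patients are needed.
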